11.3. Analysis Sets

11.3.1. Efficacy Analysis Sets

The primary analysis will be conducted in the modified intention to treat population (mITT) population, consisting of randomized participants that have either an evaluable venogram, a

confirmed episode of venous thromboembolism, or both. A sensitivity analysis will be conducted on the full analysis set (FAS) that includes all randomized participants who received any study drug; it is based on the treatment allocated (as randomized).

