11.4.3. Efficacy Analyses

11.4.3.1. Primary Efficacy Analysis

The treatment effect will be estimated using the posterior distribution of OR_{RE} . For comparison of REGN9933 versus enoxaparin, different posterior probabilities will be provided, such as $P(OR < 0.5, 0.9, 1.0, 1.1, 1.2 \text{ etc} | \text{data})$.

The entire posterior density function for the treatment effect (OR_{RE} and the OR of confirmed VTE in participants administered REGN9933 as compared to that of apixaban) will be computed, along with the cumulative posterior distribution, which quantifies evidence for all possible treatment effects. A prior for treatment difference $\log(OR) \sim N(0, 0.843)$ will be used. Bayesian summary statistics including two-sided 95% Highest Density Interval, posterior mean, and median will be reported. Summary statistics based on the raw data including the number of participants reflected in the calculation (n), mean, standard deviation, Q1, median, Q3, minimum, and maximum will be reported.

The Kaplan-Meier plot for cumulative incidence of confirmed VTE over time will be provided by treatment groups. Participants dropped out before the venogram or with missing venograms are considered as censored.

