11.4.2.	SAS Code for Stratified CMH.....	43

LIST OF TABLES

Table 1:	Efficacy/PD Analyses	35
Table 2:	Safety Analyses	36
Table 3:	Schedule of Events	37
Table 4:	Schedule of Events: Visit 2 Blood Collection	39

LIST OF FIGURES

Figure 1:	Study Flow Diagram	13
-----------	--------------------------	----

LIST OF ABBREVIATIONS AND DEFINITION OF TERMS

ADA	Anti-drug antibody
AE	Adverse event
AESI	Adverse event of special interest
ALT	Alanine aminotransferase
aPTT	Activated partial thromboplastin time
AST	Aspartate aminotransferase
ASA	Acetylsalicylic acid
ATC	Anatomical therapeutic chemical
AUC _{last}	Area under the curve computed from time zero to the time of the last positive concentration
BID	Twice daily
BMI	Body mass index
BUN	Blood urea nitrogen
Cmax	Peak concentration
CMH	Cochran-Mantel-Haenszel
CRNM	Clinically relevant non-major
DOAC	Direct oral anticoagulants
DNA	Deoxyribonucleic acid
DVT	Deep venous thrombosis
ECG	Electrocardiogram
EOT	End of test
EOS	End of study
ET	Early termination
FAS	Full analysis set
FSH	Follicle stimulating hormone
FXI	Factor XI
FXIIa	Factor XIIa
FXI:C	Factor XI functional activity
GFR	Glomerular filtration rate
IA	Interim analysis
ICF	Informed consent form
ICH	International Conference for Harmonisation
ID	Identification
ISTH	International Society on Thrombosis and Hemostasis
INR	International normalized ration

IV	Intravenous
LOQ	Limit of quantification
MCMC	Markov Chain Monte Carlo
MDRD	Modification of Diet in Renal Disease
MedDRA	Medical Dictionary for Regulatory Activities
mITT	Modified intent to treat
OR	Odds ratio
OR _{RE}	the odds ratio of confirmed VTE in participants administered REGN9933 as compared to that of enoxaparin
PCSV	Potentially Clinically Significant Value
PD	Pharmacodynamic(s)
PE	Pulmonary embolism
PK	Pharmacokinetic(s)
PRO	Patient reported outcomes
PT	Prothrombin time
RBC	Red blood cell
Regeneron	Regeneron Pharmaceuticals, Inc.
RNA	Ribonucleic acid
SAE	Serious adverse event
SAF	Safety analysis set
SAP	Statistical analysis plan
SAS	Statistical Analysis System
SC	Subcutaneous
SD	Standard deviation
SOC	System organ class
TD	Target day
TE	Treatment-emergent
TEAE	Treatment-emergent adverse event
TGA	Thrombin generation assay
TKA	Total knee arthroplasty
ULN	Upper level of normal
VTE	Venous thromboembolism
WBC	White blood cell
WHO	World Health Organization
WHODD	World Health Organization Drug Dictionary

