1.4. Modifications from the Statistical Section in the Final Protocol

There is no modification from the statistical section in the final protocol.

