5.7. Analysis of Efficacy Variables

The efficacy analyses will be performed using the mITT analysis set.

Pooling of Sites/Centers

For this multi-center study, a small number of participants are anticipated at some sites. Since these study sites may not provide appropriate information to allow the analysis, the efficacy analyses adjusted/stratified by country instead of site will be conducted.

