5.7.3. Sensitivity Analysis

To assess the robustness of the Bayesian model on the choice of prior distributions, sensitivity analyses will be performed and reported for these possible prior distributions for parameters β_0 , β_1 , and β_2 (including but not limited: $N(0,1)$, $N(0,10)$, $N(0,100)$, and $N(0,10^6)$).

A Bayesian logistic regression model with these two covariates (country and treatment group) will be explored to assess the treatment effect conditional on country only.

To assess the sensitivity of the Bayesian logistic model, the stratified Cochran-Mantel-Haenszel (CMH) method by both country and age group will be performed. The SAS code for CMH analysis is provided in Appendix 11.4.2. The stratified CMH by country only as the stratification factor will also be explored.

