6.3. Data Handling Convention for Missing Data

Missing data will not be imputed in listing. This section includes the methods for missing data imputation for some summary analyses, if necessary.

Adverse event

If the intensity of a TEAE is missing, it will be classified as “severe” in the frequency tables by intensity of TEAEs. If the assessment of relationship of a TEAE to the investigational product is missing, it will be classified as related to the investigational product.

Missing date

Every effort will be made to collect the start dates of all AEs and concomitant medications/procedures. However, in the case the start date of an AE or concomitant medication is incomplete or missing, it will be assumed to have occurred on or after the first dose of study medication, except if an incomplete date (e.g., month and year) clearly indicates that the event started prior to treatment. If the partial date indicates the same month or year of the first dose of study medication date, then the start date of the first dose will be imputed, otherwise, the missing day or month by the first day or the first month will be imputed.

Potentially Clinically Significant Value (PCSV)

If a participant has a missing baseline value, this participant will be grouped in the category “normal/missing at baseline”.

For PCSVs with 2 conditions, one based on a change from baseline value and the other on a threshold value or a normal range, with the first condition being missing, the PCSV will be based only on the second condition.

For a PCSV defined on a threshold and/or a normal range, this PCSV will be derived using this threshold if the normal range is missing; e.g., for eosinophils the PCSV is >0.5 giga/L or $>\text{ULN}$ if $\text{ULN} \geq 0.5$ giga/L. When ULN is missing, the value 0.5 should be used.

Measurements flagged as invalid by the laboratory will not be summarized or taken into account in the computation of PCSVs.

For laboratory results below the quantifiable LOQ, half of the LOQ will be imputed for calculating the descriptive summary.

No imputations for missing laboratory data, ECG data, vital sign data, or physical examination data will be made.

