11. APPENDIX

11.1. Summary of Statistical Analyses

Table 1: Efficacy/PD Analyses

Endpoint	Analysis Populations	Primary Statistical Method/Analysis	Sensitivity Analysis	Subgroup Analysis	Other Analyses
Primary Endpoint					
Proportions of participants with adjudicated, confirmed VTE through day 12	mITT	Bayesian logistic regression	Stratified CMH analysis	Yes	No
Secondary/PD Endpoints					
Secondary efficacy endpoints	mITT	Bayesian logistic regression	Stratified CMH analysis	Yes	No
aPTT, PT	PDAS	Descriptive Statistics	No	No	No
FXI:C, TGA	PDAS	Descriptive Statistics	No	No	No

Table 2: Safety Analyses

Endpoint	Analysis Populations	Statistical Method	Supportive Analysis	Subgroup Analysis	Other Analyses
Adverse Events	SAF	Descriptive Statistics	No	No	No
Laboratory Measures	SAF	Descriptive Statistics	No	No	No
Vital Signs	SAF	Descriptive Statistics	No	No	No
ECG	SAF	Descriptive Statistics	No	No	No

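### The SAP drops the protocol's full-analysis-set sensitivity analysis and Kaplan-Meier plot while declaring no change, so nothing in it tests the effect of missing or non-evaluable venograms

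*Protocol*

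**What the plan says.** Protocol 11.3.1 makes mITT the primary efficacy set and adds a firm commitment: "A sensitivity analysis will be conducted on the full analysis set (FAS) that includes all randomized participants who received any study drug", analysed as randomised. Protocol 11.4.3.1 (and the synopsis) adds a second: "The Kaplan-Meier plot for cumulative incidence of confirmed VTE over time will be provided by treatment groups", with participants lacking a venogram censored.

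The SAP carries neither forward.

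- SAP 3.1 to 3.5 define the mITT, safety, PK, ADA and PD sets. There is no FAS; the term survives only in the abbreviation list, as "Full analysis set".
- SAP 5.7: "The efficacy analyses will be performed using the mITT analysis set". SAP 5.7.2 and Table 1 in SAP 11.1 say the same for the secondary endpoints.
- SAP 5.7.3 begins: "To assess the robustness of the Bayesian model on the choice of prior distributions, sensitivity analyses will be performed and reported". It then adds a model with country and treatment only, and stratified CMH tests. Table 1 names one sensitivity analysis for the primary endpoint: "Stratified CMH analysis".
- SAP 6.3 opens: "This section includes the methods for missing data imputation for some summary analyses, if necessary". It then covers adverse events, dates, potentially clinically significant values and laboratory results, but not venograms.

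SAP 1.4 nevertheless states: "There is no modification from the statistical section in the final protocol".

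**The concern.** Protocol 3.2.1 expects most primary events to come from venography, and Protocol 9.2.2.1 foresees venograms that cannot be read. A participant enters the mITT set only with an evaluable venogram or a confirmed VTE, both determined after randomisation and with treatment known to participant and site. If those without an evaluable venogram differ in risk between arms, the primary odds ratio is biased. Every sensitivity analysis in the SAP keeps the same mITT set, so none could show by how much.

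Blinded adjudication protects the reading of images that exist. It does nothing for venograms never performed. Mandatory venography (Protocol 6.1), the willingness criterion (7.2.1), the exclusion of factors that preclude venography (7.2.2) and optional replacement (7.4) should limit missingness, but they do not measure its effect.

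**Working it through.** **1. Documents side by side.**

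| Item | Protocol | SAP |
|---|---|---|
| Sensitivity analysis on the FAS | Committed, 11.3.1 | Absent; set not defined |
| Kaplan-Meier plot | Committed, 11.4.3.1 | Absent |
| Scoring of a FAS participant without an evaluable venogram | Not given | Not given |
| Sensitivity analyses | FAS | Priors, covariates, CMH, all on mITT |
| Declared changes | n/a | None, 1.4 |

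The relevant SAP body sections (3, 5.7, 6.3, 11.1, 11.4) are intact, so the absence is not a gap in the public copy.

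**2. Inputs for scale.** From the documents: VTE rates of 13% (REGN9933) and 22.4% (enoxaparin), 120 per arm, and a log(OR) prior with 0.843. I read 0.843 as a standard deviation because ln 4 / 1.645 = 0.843 reproduces the stated 90% probability for an OR between 0.25 and 4. Assumed, because the documents give nothing: missing share m of 10, 20 or 30%, equal in both arms, and k, the risk in the missing divided by the risk in the observed. The model is unadjusted, with intercept prior N(0, 10^4), and the planned rates are taken as those observed in mITT.

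**3. Odds ratio over the whole arm.** Full-arm rate = (1 − m)p + m·k·p. With nothing missing, OR = (0.13/0.87)/(0.224/0.776) = 0.52. At m = 0.2:

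- k = 2 for REGN9933: 0.8×0.13 + 0.2×0.26 = 0.156 vs 0.224, OR 0.64.
- k = 2 for enoxaparin: 0.130 vs 0.8×0.224 + 0.2×0.448 = 0.269, OR 0.41.
- k = 2 for both: 0.156 vs 0.269, OR 0.50.

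**4. P(OR<1|data).** Grid posterior from expected counts on 120(1 − m) per arm, with the full-arm OR formed at each grid point. With nothing missing it is 0.963.

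| m | mITT | REGN9933 missing at 2× | Enoxaparin missing at 2× |
|---|---|---|---|
| 10% | 0.954 | 0.909 | 0.979 |
| 20% | 0.942 | 0.826 | 0.986 |
| 30% | 0.927 | 0.723 | 0.990 |

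With both arms at 2× and m = 20% it stays at 0.942.

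**5. Tipping points.** Risk x among missing REGN9933 participants that brings the OR to 1:

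- Missing enoxaparin at observed risk: (1 − m)0.13 + m·x = 0.224, so x = 1.07 (impossible), 0.60 and 0.44 at 10, 20 and 30% missing. At 20% that is 0.60/0.13 = 4.6 times the observed risk.
- Missing enoxaparin event-free: (1 − m)0.13 + m·x = (1 − m)0.224, so x = 0.85, 0.38 and 0.22. At 20% that is 2.9 times the observed risk.
- Missing REGN9933 at observed risk and missing enoxaparin event-free: OR 0.59, 0.68 and 0.80, so that alone does not reverse the direction.

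**6. Why a bare FAS analysis is not enough.** Counting every missing participant as event-free creates an effect when missingness differs. With 22.4% risk in both arms and 25% missing on REGN9933 against 15% on enoxaparin, 0.75×0.224 = 0.168 vs 0.85×0.224 = 0.190, OR 0.86; reversed, 1.16. With balanced missingness the same rule tests almost nothing: 12/96 vs 22/96 gives P(OR<1) 0.959 on mITT and 0.957 on 12/120 vs 22/120. Unshifted imputation given arm on the same counts returns OR 0.479 against 0.481 (20,000 draws).

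**7. The Kaplan-Meier plot.** Take one arm of 120 with 2 early events, 24 censored on day 8 and 10 of 94 positive on day 10. Cumulative incidence is 1 − (118/120)(84/94) = 12.1%, against 12/96 = 12.5% in mITT. Censoring reproduces the mITT figure closely, so the plot does not test missingness.

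**The case against.** The strongest reply is that little was lost. The protocol gives no scoring rule for a FAS participant without an evaluable venogram, so copying its sentence into the SAP would not by itself test missingness, and the simplest completion barely moves the result when missingness is balanced. That stands, and it is why the fix needs a scoring rule. A tipping-point analysis goes beyond what the protocol promised and is one good way to make the commitment usable. The Kaplan-Meier omission is a documentation matter only.

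The illustration can also be called reassuring. At 10% missing, with missing enoxaparin participants at observed risk, no REGN9933 risk reverses the direction; doubling the risk in both arms leaves the posterior unchanged. That stands too. The inputs are hypothetical and the third decimal should not be trusted: the whole-number counts nearest the planned rates (12 or 13 vs 21 or 22 of 96) give mITT posteriors of about 0.92 to 0.96, and about 0.78 to 0.87 with doubled REGN9933 risk.

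No posterior success threshold is set for the analysis; 0.95 appears only in the sample-size simulation. The shifts therefore change how the result is described, not a pre-specified decision. This limits the severity, but SAP 5.7.5 says inference is about estimation, and the odds ratio and its posterior are what the trial reports.

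Finally, central reading and blinded adjudication limit bias in judging evaluability, so venograms never done are the larger worry. None of this supplies the missing analysis or makes SAP 1.4 correct.

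**Conclusion.** The concern holds and should be fixed. The two documents conflict on two committed outputs, SAP 1.4 is incorrect, and an analyst following the SAP would produce no check on missing or non-evaluable venograms. The textual finding rests on no assumption. Its numerical consequence cannot be known from the documents. Under the assumptions above (equal missingness, planned rates in mITT, unadjusted model, prior SD 0.843), a doubled risk confined to one arm's missing participants moves P(OR<1|data) from 0.94 to between 0.83 and 0.99 at 20% missing, and the OR from 0.52 to between 0.41 and 0.64. Effect size and posterior probability are more exposed than direction. The choice of mITT as the primary set is not disputed.

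**What to change.** 1. Define the FAS in SAP Section 3 and add the primary model on the FAS to SAP 5.7.3 and Table 1.
2. State the scoring: confirmed VTE through day 12 is an event; an evaluable negative venogram without VTE is a non-event; anything else is missing. Do not count all missing as event-free.
3. For the missing, specify a tipping-point analysis that varies the assumed risk separately by arm and in both directions, for example 0.5 to 2 times the arm's observed risk plus the event-free and all-event bounds. Report the OR and P(OR<1|data) at each point and where the OR crosses 1. Imputation from arm, country and age group alone will essentially return the mITT estimate unless the imputed risk is shifted.
4. Tabulate by arm the number of, and reasons for, venograms not done and venograms not evaluable, kept separate.
5. Add the Kaplan-Meier plot to the SAP, or declare and justify its removal, without presenting it as a missing-data check.
6. Correct SAP 1.4 to list these changes. It should also list three other differences: the 95% highest density interval in Protocol 11.4.3.1 against the 90% credible interval in SAP 5.7.1; the mITT definition, which in SAP 3.1 adds treatment and a day 12 limit; and the interim trigger, finished study in Protocol 11.5 against evaluable primary endpoint in SAP 7.

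The cost is SAP wording and a few extra tables. No new data and no protocol change are needed, and SAP Section 1 allows documented revision before database lock.

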11.3.2. Safety Analysis Set

The safety analysis set (SAF) includes all randomized participants who received any study drug; it is based on the treatment received (as treated). Treatment compliance/administration and all clinical safety variables will be analyzed using the SAF.

11.3.3. Pharmacokinetic Analysis Sets

The PK analysis population includes all participants in the REGN9933 treatment group who received study drug and who had at least 1 non-missing result following the first dose of study drug.

11.3.4. Immunogenicity Analysis Sets

The ADA analysis set includes all participants who received study drug and had at least 1 non-missing ADA result following the first study dose.

11.3.5. Pharmacodynamic Analysis Set

The pharmacodynamic analysis set includes all randomized participants who received any study drug and who had at least 1 non-missing PD result following the first dose of study drug; it is based on the treatment received (as treated).

11.4. Statistical Methods

For continuous variables, descriptive statistics will include the following information: the number of participants reflected in the calculation (n), mean, standard deviation, Q1, median, Q3, minimum, and maximum.

For categorical or ordinal data, frequencies and percentages will be displayed for each category.

11.4.1. Participant Disposition

The number and percentage of participants screened, randomized, and the primary reasons for screening failure and discontinuation will be summarized.

11.4.2. Demography and Baseline Characteristics

Demographic variables (eg, age, race, and gender), baseline characteristics, medical history, and prior and concomitant medications and therapies will be summarized by treatment group. See Section 5.1 for a full list of demographic and baseline variables. No statistical hypothesis tests will be performed on these characteristics.

11.4.3. Efficacy Analyses

11.4.3.1. Primary Efficacy Analysis

The treatment effect will be estimated using the posterior distribution of OR_{RE} . For comparison of REGN9933 versus enoxaparin, different posterior probabilities will be provided, such as $P(OR < 0.5, 0.9, 1.0, 1.1, 1.2 \text{ etc} | \text{data})$.

The entire posterior density function for the treatment effect (OR_{RE} and the OR of confirmed VTE in participants administered REGN9933 as compared to that of apixaban) will be computed, along with the cumulative posterior distribution, which quantifies evidence for all possible treatment effects. A prior for treatment difference $\log(OR) \sim N(0, 0.843)$ will be used. Bayesian summary statistics including two-sided 95% Highest Density Interval, posterior mean, and median will be reported. Summary statistics based on the raw data including the number of participants reflected in the calculation (n), mean, standard deviation, Q1, median, Q3, minimum, and maximum will be reported.

The Kaplan-Meier plot for cumulative incidence of confirmed VTE over time will be provided by treatment groups. Participants dropped out before the venogram or with missing venograms are considered as censored.

11.4.4. Control of Multiplicity

Not applicable.

11.4.5. Safety Analysis

Safety will be assessed by clinical and statistical review of all relevant parameters, including vital signs, physical examinations, ECGs, laboratory evaluations, and AEs.

11.4.5.1. Adverse Events

Definitions

For safety variables, the 3 observation periods are defined in Section 9.1. Treatment-emergent adverse events are defined as those that are not present at baseline or represent the exacerbation of a pre-existing condition after the dose administrations.

Analysis

Summaries of all TEAEs by treatment group will include:

- The number (n) and percentage (%) of participants with at least 1 TEAE by SOC and PT
- TEAEs by severity (according to the grading scale outlined in Section 10.2.5), presented by SOC and PT
- Treatment-emergent AESIs
- Treatment-emergent adverse events leading to permanent treatment discontinuation will be summarized by treatment group.

11.4.5.2. Other Safety

Vital Signs

Vital signs (temperature, pulse, blood pressure, and respiration rate) will be summarized.

Laboratory Tests

Laboratory test results will be summarized.

Number and percentage of participants with a potentially clinically significant value will be tabulated.

11.4.5.3. Treatment Exposure

The duration of exposure during the treatment period will be presented by treatment group and calculated as:

- For participants assigned to the enoxaparin or apixaban arm, exposure will be summarized by the number of days that the subject received enoxaparin or apixaban administrations.

11.4.5.4. Treatment Compliance

The compliance with study treatment will be calculated as follows:

$$\text{compliance \%} = 100\% \times \frac{\text{number of actual administrations}}{\text{number of planned administrations}}$$

The number of planned administrations will be calculated as:

- For participants assigned to the enoxaparin arm, the number of planned administrations is the number of days in the on-treatment period
- For participants assigned to the apixaban arm, the number of planned administrations is two times of the number of days in the on-treatment period
- For participants assigned to the REGN9933 arm, the number of planned administrations is one

11.4.6. Pharmacokinetics

11.4.6.1. Analysis of Drug Concentration Data

The PK parameters may include, but are not limited to:

- C_{\max} – peak concentration
- AUC_{last} -area under the curve computed from time zero to the time of the last positive concentration

The concentrations of total REGN9933 over time and selected PK parameters will be summarized by descriptive statistics for each of the treatment groups for the purpose of estimating exposures in these groups. This descriptive statistical assessment will include the geometric means and ratios of the geometric means for selected PK parameters, as deemed appropriate.

No formal statistical hypothesis testing will be performed.

